Appendix 2: Date Imputation Rules

Incomplete dates for symptom onset or initial IH Diagnosis

Partial symptom onset or IH diagnosis dates are set to the earliest possible date (i.e. first day of month if any day unknown or 1st January if any day and month are unknown).

Incomplete Adverse Event Onset Date

If *year* is missing (or completely missing): set to the date of first dose.

If (*year* is present and *month* and *day* are missing) or (*year* and *day* are present and *month* is missing):

 If *year* = year of first dose: set the date to the first dose date.

 If *year* < year of first dose: set *month* and *day* to December 31st.

 If *year* > year of first dose: set *month* and *day* to January 1st.

If *month* and *year* are present and *day* is missing:

 If *year* = year of first dose, and:

 If *month* = month of first dose: set *day* to day of first dose.

 If *month* < month of first dose: set *day* to last day of *month*.

 If *month* > month of first dose: set *day* to 1st day of *month*.

 If *year* < year of first dose: set *day* to last day of month.

 If *year* > year of first dose: set *day* to 1st day of month.

For all other cases: set to date of first dose.

Incomplete Concomitant Medication Start Date

If *year* is missing (or completely missing): do not impute.

If (*year* is present and *month* and *day* are missing) or (*year* and *day* are present and *month* is missing):

 Set *month* and *day* to January 1st.

If *year* and *month* are present and *day* is missing:

 Set *day* to 1st day of month.

Incomplete Concomitant Medication End Date

Do not impute if Ongoing Flag is checked.

If *year* is missing (or completely missing): do not impute.

If (*year* is present and *month* and *day* are missing) or (*year* and *day* are present and *month* is missing):

Set *month* and *day* to December 31st.

If *year* and *month* are present and *day* is missing:

Set *day* to last day of the month.

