6.15.6. Adverse Event and Serious Adverse Event Recording and Reporting Timeframe

The Investigator must record all AEs, and report all SAEs, that occur during the study from the time written informed consent is obtained until the final study visit or Early Termination, regardless of their relationship to study drug or procedure.

If the Investigator becomes aware of an SAE within 30 days after the last dose of study drug, the event must also be reported.

In addition, any SAE assessed as related to study drug or procedure by the Investigator must be reported regardless of time after study termination.

SAEs and immediately reportable experiences must be reported within 24 hours of first knowledge of the event by study personnel as described in Section 6.15.2 and [Section 6.15.5](#).

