10.2. Adverse Events

Adverse events (AEs) occurring from the initial subject ICF signature date until the final study visit will be reported. If the Investigator becomes aware of a serious adverse event (SAE) within 30 days after the last dose of study drug, the event must also be reported. In addition, any SAE assessed as related to study drug or procedure by the Investigator must be reported regardless of time after study termination.

AEs will be coded to system organ class (SOC) and preferred term using the Medical Dictionary for Regulatory Activities (MedDRA), Version 19.1. The investigator will assess the relationship of each AE to study drug. AE with a missing relationship to study drug will be reported as related in the summaries. Severity, as determined by the Investigator, will be classed as mild, moderate, severe, life-threatening or fatal. AE with missing severity will be reported as missing in the summaries.

Note that subjects who acquire COVID-19 or report AEs due to the COVID-19 public health emergency (e.g. anxiety) while on study will be coded accordingly and included in the adverse event summaries.

All AEs will be classified according to the period onset as defined by the following:

- Screening AEs are defined as AEs that started on or after the signature of the initial subject ICF but prior to or on the first dose of OTTP study drug
- Treatment period AEs will be defined as occurring in treatment periods (OTTP, SDP, DBRW, and OLE) based on the onset date and the date of first dosing in each of the treatment periods. AEs that occur on the start of the SDP and DBRW are attributed to the previous period.
- Safety follow-up AEs are defined as occurring after the last dose date until 30 days after the last dose date

A treatment-emergent adverse event (TEAE) is defined as any event with onset date on or after the first dose of study drug, including adverse events that occur until 30 days after the last dose date. For the purpose of calculating treatment emergence, incomplete onset dates will be imputed as detailed in Appendix 2.

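### SAP Appendix 2 imputes partial AE onset dates without looking at the end date, so an event recorded as over before the first dose can be counted as treatment-emergent

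*SAP*

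**What the plan says.** **Onset imputation (SAP Appendix 2).** Three kinds of incomplete onset are moved to the first-dose date:

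- Day missing, same month and year as the first dose: "If *month* = month of first dose: set *day* to day of first dose".
- Month missing, same year: "If *year* = year of first dose: set the date to the first dose date".
- Year or whole date missing: "If *year* is missing (or completely missing): set to the date of first dose".

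The closing catch-all does the same. An onset in an earlier month of the same year is treated differently: "If *month* < month of first dose: set *day* to last day of *month". None of the AE branches mentions the end date.

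**Treatment emergence (SAP 10.2).** A TEAE is "any event with onset date on or after the first dose of study drug", and for this purpose "incomplete onset dates will be imputed as detailed in Appendix 2". The same section defines Screening AEs to include an onset on the day of the first dose.

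**Protocol definition (section 9.9.3.1).** A TEAE began, or got worse, after the first dose. SAP 7.6 lists no change to this.

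**Stop dates (SAP 7.2.5).** Missing AE start and stop dates are to be imputed, solely to sort events into before, during and after treatment. Appendix 2 gives an end-date rule for medications but none for AEs.

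**Collection (Protocol 6.15.6).** AEs are recorded "from the time written informed consent is obtained until the final study visit or Early Termination", so events that start and finish in screening are in the database.

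**The concern.** Setting an unknown onset to the first dose is a sensible conservative choice when the timing really is uncertain. It is not sensible when the record shows that the event was over before any JZP-258 was taken. In that case the rule overrides known information, produces an onset later than the event's own end, and attributes to treatment something treatment cannot have caused.

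At stake is the accuracy of the TEAE counts in the across-study summaries, and their agreement with the protocol definition. An event that ended before dosing can neither begin nor worsen afterwards. A misclassified event would also be easy to overlook: imputed dates are kept out of the listings (SAP 7.2.5) and only non-TEAEs are flagged there (SAP 10.2), so it would simply appear without a flag.

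**Working it through.** The plan gives no figure to reproduce. The check has two parts.

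**1. The rules applied as written.** Take an illustrative first dose on 20 June 2019.

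| Recorded onset | Recorded end | Imputed onset | TEAE under SAP 10.2? |
|---|---|---|---|
| June 2019, day missing | 12 June 2019 | 20 June 2019 | Yes |
| 2019, month and day missing | 12 June 2019 | 20 June 2019 | Yes |
| Wholly missing | 12 June 2019 | 20 June 2019 | Yes |
| May 2019, day missing | 2 June 2019 | 31 May 2019 | No |
| 2018, month and day missing | 2 January 2019 | 31 December 2018 | No |

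In the first three rows the imputed onset is 20 − 12 = 8 days after the recorded end. Under the protocol's wording (after the first dose) none of the five would be a TEAE. With an end-date check the first three become pre-treatment and the last two keep their classification.

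**2. How often the day-missing branch applies.** Inputs: screening of 14 to 30 days (Protocol 3.1.1), which can be extended by 2 weeks with the Medical Monitor's permission (Protocol 7.1.1), giving 30 + 14 = 44 days. Assumptions, not in the documents: onset uniform over screening, first dose uniform over a 365-day year, and event duration of *D* days counting the onset day.

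An event starting *k* days before the first dose is over before dosing only if *k* ≥ *D*. In a month of *n* days, *n* − *k* first-dose dates (none if negative) have that onset in the same month. For screening length *L*, summing over *k* = *D* to *L* and over 12 months:

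share = [365(*L* − *D* + 1) − 12 Σ*k*] / [365(*L* − *D* + 1)]

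For *L* = 30, add 3 to the numerator, because February has no day 29 or 30.

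- *L* = 14, *D* = 1: (5110 − 12×105)/5110 = 3850/5110 = 75%
- *L* = 14, *D* = 7: (2920 − 12×84)/2920 = 1912/2920 = 65%
- *L* = 14, *D* = 10: (1825 − 12×60)/1825 = 1105/1825 = 61%
- *L* = 30, *D* = 1: (10950 − 12×465 + 3)/10950 = 5373/10950 = 49%
- *L* = 30, *D* = 7: (8760 − 12×444 + 3)/8760 = 3435/8760 = 39%
- *L* = 30, *D* = 10: (7665 − 12×420 + 3)/7665 = 2628/7665 = 34%

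Onsets more than 30 days back never share the month, so for *L* = 44 the numerators are those of *L* = 30: 5373/16060 = 33% for one-day events and 2628/12775 = 21% for ten-day events.

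If the month is missing as well, the branch applies whenever onset and first dose share a calendar year. For one-day events that is (5110 − 105)/5110 = 98% and (10950 − 465)/10950 = 96%. If the year is missing, it always applies.

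These are shares of resolved screening events with an incomplete onset date, not of all AEs.

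**The case against.** The strongest reply is that this hardly matters. An error needs an AE in screening, an incomplete onset date, a month matching the first dose (or no month or year), and an end date known to precede dosing. AEs are recorded at the Screening and Baseline visits, normally a few weeks apart, so a missing year is hardly plausible. Safety is descriptive, the direction is to over-report harm, and the actual end date stays in the listings, so an event can be traced. All of this stands. It limits the size of the problem but does not supply the missing condition; no other section excludes such an event.

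A reader might also draw four stronger conclusions that the documents do not support:

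- *That half to three quarters of resolved screening AEs with a missing day are affected.* That range holds only for one-day events. It falls with longer events, because an event that has resolved must have started earlier, and it falls with extended screening.
- *That the event would appear in the week 1 row of SAP 10.2.2.* SAP 10.2 also classes an onset on the first-dose date as a Screening AE, and the SAP does not say which definition governs that row. The overlap does not remove the event from the TEAE count, because the TEAE definition stands by itself.
- *That the listings would show an onset after the end date.* SAP 7.2.5 keeps imputed dates out of the listings.
- *That the randomised comparison is distorted.* Read with SAP 10.2, the imputation goes to the first dose of study drug, which is open-label and weeks before randomisation.

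**Conclusion.** The point holds as a minor one. As written, Appendix 2 together with SAP 10.2 classifies as treatment-emergent an event that the record shows ended before dosing. That contradicts the protocol's TEAE definition and leaves unfulfilled the statement in SAP 7.2.5 that AE stop dates will serve the classification.

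Given a resolved screening event with only the onset day missing, the chance of misclassification is roughly 34% to 75% for events of one to ten days with 14 to 30 days of screening, and 21% to 33% at 44 days. These figures rest on the uniform-onset and uniform-first-dose assumptions and on assumed durations. The documents give no count of incomplete dates, so the number of events cannot be estimated; it is probably small.

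The effect is confined to descriptive, non-randomised TEAE summaries. Efficacy, the double-blind safety comparison and all hypothesis tests are untouched.

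**What to change.** Add to the AE onset rules in SAP Appendix 2:

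1. If the AE end date, whether complete or partial but unambiguous, is before the first dose, the event is not treatment-emergent.
2. An imputed onset is never later than the end date. Otherwise the existing rules apply.
3. A rule for incomplete AE stop dates, as SAP 7.2.5 announces.

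It would help to state in SAP 10.2 whether an onset on the first-dose date belongs to screening or to the titration period for the by-period and by-interval tables.

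The cost is a few sentences and a small programming change. Items 1 and 2 can only lower TEAE counts, and only by events shown to have ended before dosing, so no genuine treatment-emergent event is lost. The stop-date rule in item 3 should be written so that an ambiguous end date does not by itself make an event pre-treatment.

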Appendix 3: Listing of Stimulant or Alerting Agents

The following standardized WHO dictionary medication names are considered stimulant or alerting agents:

Dextroamphetamine - amphetamine salt
Lisdexamfetamine Mesilate
Methamphetamine
Dexmethylphenidate
Methylphenidate
Methylphenidate Hydrochloride
Armodafinil
Modafinil
Pitolisant
Mazindol
Atomoxetine
Bupropion
Epinephrine
Phenylephrine Hydrochloride
Solriamfetol

This list of stimulant or alerting agents can be updated as the study progresses. All recorded medications will be reviewed by clinical development on an ongoing basis. The final list of stimulant or alerting agents will be maintained by data management.

Appendix 4: List of Clinical Laboratory Test

Subjects will be in a seated or supine position during blood collection. Clinical laboratory tests will include the following as listed in Table . Clinical laboratory tests will be performed at the times indicated in Appendix 1 of the study protocol.

Table 6: List of Laboratory Tests

Laboratory Test	Parameters
Hematology	
 • Complete blood count (CBC) • Platelet count (PLT) • White blood cell count (WBC) with differential • Hemoglobin (HGB) • hematocrit (HCT) • Red blood cell count (RBC) • Mean corpuscular volume (MCV) • Mean corpuscular hemoglobin (MCH) • Mean corpuscular hemoglobin concentration (MCHC) • Red cell distribution width (RDW)
Urinalysis^b	
 • Appearance • Bilirubin • Color • Glucose • Ketones • Nitrite • Occult blood • pH • Protein • Specific gravity • Urobilinogen
Serum Chemistry	
 • Albumin (ALB) • Alkaline phosphatase (ALK-P) • Alanine aminotransferase (ALT; SGPT) • Aspartate aminotransferase (AST; SGOT) • Blood urea nitrogen (BUN) • Calcium (Ca) • Chloride (Cl) • Creatinine • Gamma-glutamyl transferase (GGT) • Globulin • Glucose • Phosphorus • Potassium (K) • Sodium (Na) • Magnesium • Total bilirubin • Direct bilirubin • Total cholesterol • Total protein • Triglycerides • Uric acid • Thyroid stimulating hormone (TSH)(Screening only)
Pregnancy Screen^a	
 • Serum at the Screening Visit, the End of Stable Dose Visit, and the End of the Open-label Extension Visit / Early Termination. • Urine at all other clinic visits (scheduled or unscheduled or as required by local regulations). • In each case of delayed menstrual period (over one month between menstruations) in women of child-bearing potential, a pregnancy test must be performed. This applies to WOCBP with infrequent or irregular menstrual cycles.
Drug Screen	
 • Urine drug screen at all clinic visits during the study. • Breath alcohol test at all clinic visits during the study.

^aPregnancy screening is required for all women of childbearing potential. A woman is considered of childbearing potential (i.e., fertile) following menarche until becoming postmenopausal unless permanently sterile. Permanent sterilization methods include hysterectomy, bilateral salpingectomy, and bilateral oophorectomy. A postmenopausal state is defined as no menses for 12 months without an alternative medical cause.

^bPerform reflex microscopy for dipstick positive for blood, nitrite, or protein.

Appendix 5: Change in events when site visits must be converted to remote visits

Assessment (Per Protocol Appendix 1: Schedule of events)	Conduct Remotely (Telephone or videoconference)	Mail to Subject, as applicable	Perform when Subject Next Able to Safely Return to an On-site Visit
Physical Exam			X
Weight			X
Vital Signs			X
Hematology, Chemistry			X
Urinalysis			X
Urine drug screen			X
Breath alcohol test			X
Serum pregnancy test			X
Urine pregnancy test		X	
12-lead ECG			X
Review sleep diary and VAS for Sleep inertia	X		
ESS	X		
CGIc	X		
PGIc	X		
IHSS	X		
FOSQ-10	X		
WPAI:SHP	X		
C-SSRS Since Last Visit Version	X		
Review Study Drug Dosing Diary for completeness and compliance	X		
Assess subject and determine if additional dose titration is necessary	X		
Dispense Study Drug		X	
Collect Study Drug, Measure compliance	X*		X*
AE Reporting	X		
Concomitant Medications	X		

*Sites will discuss with subject the amount of drug taken and amount remaining in bottles at time of telephone visits. But final compliance calculations will be made at next on-site visit when bottles are returned.

The safety assessments performed at every on-site visits are weight, vital signs, urine drug screen, breath alcohol test and urine pregnancy test and will be considered missed at remote visits.

AE=Adverse Event; C-SSRS: Columbia Suicide Severity Rating Scale; CGIc=Clinical Global Impression of Change; DBRW= Double-Blind Randomized Withdrawal Period; ECG=electrocardiogram; ESS=Epworth Sleepiness Scale; FOSQ-10= Functional Outcomes of Sleep Questionnaire; IH=Idiopathic Hypersomnia; IHSS=Idiopathic Hypersomnia Severity Scale; PGIC= Patient Global Impression of Change; SDP=Stable Dose Period; TST=Total Sleep Time; VAS=Visual Analog Scale; WPAI:SHP=Work Productivity and Activity Impairment Questionnaire: Specific Health Problem.
